  - Investigational Device Instructions for Use
  - Deviation/Violation Log
  - EPIC-Norfolk Food Frequency Questionnaire (FFQ)
  - Modifiable Activity Questionnaire (MAQ)
  - Case Report Forms
  - Example of Quality of Life Survey

### Safety Reporting

Safety reporting responsibilities to Sponsor as follows

	Who	When	How	To Whom
SAE	Investigator or Sponsor	Within 15 days of becoming aware of the event	SAE report form	Main IEC/REC for the investigation
Urgent Safety Measures	Investigator or Sponsor	Immediately	By Telephone, follow up written communication	Main IEC/REC for the investigation
Urgent Safety Measures	Exceptionally by local investigator	Within three days	In writing reason for the urgent safety measures and plan for further action/follow up	Main REC for the investigation

Vestibular Stimulation to Trigger Adip Clinical Trial Project Name	112 of 112
Clinical Protocol for VeS	
243973(NI)_181094(UCSD USA) Study Reference Number	11 Revision Number

## **Neurovalens Limited**

Clinical Study Identifier: 243973

Identifier: EXP18020

Audit Trail For This Document				
Compiled by/ Affiliation	Type of Change	Date	Version	
[name]	Initial Version Issued and Signed	27JUN2019	1.0	
[name]	Updates following FDA advice	28OCT2019	1.1	
GEM Programming Solutions statistics team	Changed ordering of secondary endpoints for label claims, alignment with protocol updates, alignment with FDA advice on VeSTAL DM study SAP, and clarifications prior to database lock	01JUN2022	1.2	
Effective Date		15JUN2022		

## **Neurovalens Limited**

Identifier: EXP18020 Clinical Study Identifier: 243973

## Neurovalens Limited Identifier: EXP18020

Clinical Study Identifier: 243973

#### **ABBREVIATIONS**

ACTRI Altman Clinical and Translational Research Institute

ADE Adverse Device Event

AE Adverse Event

BOCF Baseline Observation Carried Forward

BMC Bone Mineral Content
BMI Body Mass Index
CRF Case Report Form
CTM Clinical Trial Mentors

DXA Dual Energy X-Ray Absorptiometry

EPARC Exercise and Physical Activity Resource Center

EU European Union

FDA Food and Drug Administration (United States)

FFQ Food Frequency Questionnaire

G Grams

HbA1c Glycated Hemoglobin
HDL High Density Lipoprotein
HEI Healthy Eating Index
ITT Intention To Treat

IWQOL Impact of Weight on Quality Of Life

Kg Kilograms

LOCF Last Observation Carried Forward

LS Least Squares

MMRM Mixed Model with Repeated Measures

PP Per Protocol

SAE Serious Adverse Device Event

SAE Serious Adverse Event
SAP Statistical Analysis Plan
SAS Safety Analysis Set

SAS® Statistical Analysis System

SD Standard Deviation

SOP Standard Operating Procedure

TDE Texas Diabetes and Endocrinology

TFLs Tables, Figures and Listings

UCSD University of California San Diego

USA United States of America
UU University of Ulster
VAT Visceral Adipose Tissue
VeNS Vestibular Nerve Stimulation

WST We Slim Together

Identifier: EXP18020 Clinical Study Identifier: 243973

#### 1. INTRODUCTION

Neurovalens are conducting a randomized, double blind, sham controlled clinical trial to evaluate the efficacy and safety of non-invasive electrical vestibular nerve stimulation (VeNS), together with a lifestyle modification program, as a method of reducing excess body weight. The study will be randomized using a parallel assignment in a 1:1 active to control allocation, whereby the active group will use the vestibular nerve stimulation (VeNS) device, combined with a lifestyle modification program, and the control group will receive a sham device, combined with a lifestyle modification program. The study aims to recruit a total of 200 participants, across two or three sites, with a dropout allowance of 10% to generate a minimum of 90 active treatment and 90 control subjects. The study will be double blinded, meaning that both the subjects and outcome assessors will be blind to device assignment until the end of the visit at the 6 month timepoint.

For the purposes of the final analysis, the treatment assignment will be unblinded to all study personnel such that inferences can be made as to the efficacy and safety of the vestibular nerve stimulation (VeNS) device, in comparison to a sham control. The study will last approximately 6 months in total for each participant. The final analysis will be conducted at the 6 month timepoint. All subjects will cease involvement in the trial after the 6 month blinded period.

This document outlines the process followed by the study team to conduct the final analysis, along with the planned efficacy and safety analyses designed to fulfill the study objectives. As specified in the study protocol, it is noted that the criteria to meet the primary objective, to establish the clinical performance of the VeSTAL device stimulation effect in subjects who are overweight, differ between the EU and USA regulatory clearance pathways. As a result, this document clearly defines the proposed analyses and success criteria for both the EU and USA regulatory clearance pathways in the relevant sections. The secondary efficacy and safety objectives are shared by both regulatory pathways and therefore will follow the same analysis plan once the primary objective has been evaluated.

Note that the version 1.1 of this SAP that was originally discussed and agreed with FDA was authored by Exploristics Ltd; GEM Programming Solutions Ltd, who will be conducting the analyses, made further updates and clarifications in version 1.2 of this SAP prior to database lock.

#### 2. STUDY OBJECTIVE(S) AND ENDPOINT(S)

## 2.1 Study Objective(s)

The primary objective of the study is to establish the clinical performance of the VeSTAL device stimulation effect in subjects who are overweight. The clinical performance will be evaluated in terms of the efficacy of the VeSTAL device, in comparison to the sham control.

Secondary objectives of the study will include evaluations of the safety and tolerability of the VeSTAL device, relative to the sham control group, in terms of the occurrence of adverse events, change from baseline in vital signs, hearing tests and treatment exposure.

Identifier: EXP18020 Clinical Study Identifier: 243973

## 2.2 Study Endpoint(s)

## 2.2.1 Primary Efficacy

The primary efficacy endpoints, which will be analyzed at 6 months in order to quantify the efficacy of the VeSTAL device, differ between regulatory clearance pathways.

For the purpose of the *USA regulatory clearance pathway*, the efficacy of the VeSTAL device will be quantified by two primary endpoints:

- 1. Mean percentage weight loss in comparison to the sham control
- 2. Proportion of participants who lose at least 5% body weight

For the purpose of the *EU regulatory clearance pathway*, the efficacy of the VeSTAL device will be quantified based on a single primary endpoint:

1. Mean percentage weight loss in comparison to the sham control

## 2.2.2 Secondary Efficacy

The secondary efficacy endpoints will be consistent between regulatory clearance pathways and will include further analyses of percentage weight loss, fat loss, subject reported outcomes for quality of life, diet and activity, certain blood assays and changes in concomitant medications. These secondary endpoints will be analyzed at the 6 month timepoint.

### 2.2.2.1 Labelling Claims

Statistical comparisons between the VeSTAL and Sham control device treatment groups will be performed on percentage weight loss in the follow-up period, percentage fat loss, DXA measurements, dietary outcomes, quality of life measures, and blood parameters. These endpoints will be used to support the following seven labeling claims which will be tested sequentially, after the primary endpoints, in the following order:

At the 6 month timepoint

- 1. Percentage visceral adipose tissue (VAT) loss
- 2. Percentage change in low density lipoprotein (LDL)
- 3. Percentage fat loss
- 4. Percentage change in lean muscle mass
- 5. Change in Atherogenic index
- 6. Change in Systemic inflammation
- 7. Change in Total calorie intake
- 8. Change in Quality of Life total score

VAT loss, fat loss and lean muscle mass are measured by body DXA scanning. The atherogenic index will be determined by the ratio of total cholesterol to HDL. Systemic inflammation and quality of life

Neurovalens Limited Identifier: EXP18020

Clinical Study Identifier: 243973

are measured by high-sensitivity C-reactive protein and the IWQoL questionnaire respectively. Total calorie intake will be measured using the two-day 24-hour dietary recall.

## 2.2.2.2 Other secondary endpoints

The efficacy of the VeSTAL device will be evaluated further by performing statistical comparisons between treatment groups on the following secondary efficacy endpoints:

- Percentage trunk fat loss
- Percentage bone mineral content (BMC) gain

The questionaire data, inclusive of the two-day 24-hour dietary recall and modifiable activity questionnaire, will be summarized per treatment group and time point in support of the efficacy findings. Additionally, changes in cardiovascular and initiation of diabetic medications will be summarized in terms of an increase, decrease or no change in concomitant medication. Medications will also be summarized by treatment according to potential impact on weight status. These will be classified as medications that could potentially cause either weight gain or weight loss as deemed by the Chief Investigator.

### 2.2.3 Safety

The safety of subjects will be assessed through summaries and descriptive comparisons between treatment groups on the following safety data:

- Laboratory Data
  - Fasting glucose
  - Glycated hemoglobin (HbA1c)
- Vital Signs
  - Blood pressure
  - Heart rate
  - Waist and hip circumferences
  - Body Mass Index (BMI)
- Adverse Event and Quality of Life Data
  - Frequency of Adverse Events (AE) and Adverse Device Events (ADE)
  - o Adverse event monitoring questionnaire
  - Outcome of hearing loss assessments

Identifier: EXP18020 Clinical Study Identifier: 243973

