# 6.13 Serum Assays

Venous blood assays, with the subjects in a fasted condition, will be carried out at 0 and 6 months for glucose, HbA1c, lipid profile and high sensitivity CRP (hs-CRP). These are being analyzed as secondary (i.e. hypothesis generating) endpoints. The purpose in choosing these specific assays is to screen for change in cardiovascular risk factors. Specifically, glycemic control, lipid profile and inflammation are assessed using these tests. There is an increasing appreciation of the value of hs-CRP in assessing inflammation as a marker of cardiovascular

Vestibular Stimulation to Trigger Adip Clinical Trial Project Name	47 of 112		
Clinical Protocol for VeSTAL			
243973(NI)_181094(UCSD USA) Study Reference Number	Protocol Document Type	01 Document Number	11 Revision Number

risk (Fonseca and Izar, 2016). The drug trials for liraglutide (Wadden et al., 2013), lorcaserin (Smith et al., 2010) and naltrexone/bupropion (Apovian et al., 2013) all demonstrated a statistically significant improvement in hs-CRP with treatment.

All subjects are provided with an iPod touch. This contains the following pre-installed applications: the VeSTAL study app that allows the device to be controlled via Bluetooth; the Activity Tracker Pedometer app; the Facebook app; and as PDFs in the iBooks app the Instructions for Use (IFU) for the study device, a Device Use Schematic and the Physical Guidelines for Americans from the US Department of Health (see: https://health.gov/paguidelines/pdf/paguide.pdf).

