### Secondary Outcome Measures USA and EU (At 6 months):

Vestibular Stimulation to Trigger Adipose Loss (VeSTAL) Clinical Trial Project Name				69 of 112
Clinical Protocol for VeSTAL				
	Document Title			
	243973(NI)_181094(UCSD USA)	Protocol	01	11
	Study Reference Number	Document Type	Document Number	Revision Number

- The difference in mean fat mass loss (in grams) between the active-product and sham-treated groups is statistically significant. (As measured by means of a whole body DXA scan).
- The difference in mean trunk fat loss (in grams) between the active-product and sham-treated groups is statistically significant. (As measured by means of a whole body DXA scan).
- The difference in mean visceral adipose tissue (VAT) mass loss (in grams) between the activeproduce and sham-treated groups is statistically significant. (As measured by the whole body DXA scan).
- Difference in mean lean mass gain (in grams) between the active-product and sham-treated groups is statistically significant. (As measured by means of a whole body DXA scan).
- Difference in mean bone mineral content (BMC) gain (in grams) between the active-product and sham-treated groups is statistically significant. (As measured by means of a whole body DXA scan).
- Fasting glucose
- Lipid profile (Assess total non-HDL cholesterol, and HDL to total cholesterol ratio)
- High-sensitivity C-reactive protein
- Glycated hemoglobin (HbA1c)
- Two-day 24-hour dietary recall
- Modifiable activity questionnaire
- Blood pressure
- Heart rate
- Waist and hip circumferences (This will only be performed at the USA sites.)
- Body Mass Index (BMI)
- Quality of life IWQOL-Lite questionnaire.
- Dose response analysis: it is likely that some subjects will not utilize their device for the mandated 7 hours per week. Usage data will be available from the devices permitting a dose response analysis, which will done be in an intention to treat manner.
- Adjustment of medication both reduction and new medications.
- Mentor support group usage (total hours).

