### Methods: Secondary Aims

Vestibular Stimulation to Trigger Adip Clinical Trial Project Name	93 of 112
Clinical Protocol for VeS	
243973(NI)_181094(UCSD USA) Study Reference Number	11 Revision Number

For each continuous and categorical variable at each time point, we will use a two-sample t-test and Fisher's exact test, respectively. Summary statistics (mean, standard deviation, quantiles, counts, and percentages) and plots will be produced for all demographic and study outcomes. We will investigate the effectiveness of the device by usage by including usage time as a continuous covariate in a linear model for total fat loss. Statistical personnel will conduct all analyses using the latest version of R (R Foundation for Statistical Computing, Vienna, Austria. http://www.R-project.org/).

We will analyze mean fat loss in the same way as TBWL as a continuous measure with t-tests, linear regression and linear mixed effects models.

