### 12.2 Safety

The safety of the VeSTAL and Sham devices will be evaluated using descriptive summaries of safety data, with all analyses performed on the Safety Analysis Set.

A summary of treatment emergent Adverse Events (AE) and Adverse Device Events (ADE) will be provided for both the VeSTAL device and sham control treatment groups. Separate summaries will be provided, per treatment group, for any Serious Adverse Events (SAEs or SADEs) or causally related adverse events which occur on study.

Summaries of responses from the Adverse Event Monitoring Questionnaire at 1, 3, 6 months (where available), will be summarized per treatment group and time point. Additionally, the outcomes of hearing and ear canal assessments, performed at baseline, and 6 months will be summarized in order to detect any signs of deterioration which may occur whilst using the devices.

Laboratory data and vital signs as listed in section 2.2.3 will be summarized per treatment group at baseline and per time point on study. Additionally a summary of change from baseline for each of the laboratory tests will be presented over time.

Questionnaire responses for the quality of life – IWQOL-Lite questionnaire will be summarized per treatment group and time point.

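### Fasting glucose, HbA1c, non-HDL cholesterol and waist/hip are between-arm secondary outcomes in the protocol, but the SAP specifies no ITT treatment difference or confidence interval for any of them

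*SAP*

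**What the plan says.** **Protocol.** Section 18.3 lists the 6-month secondary outcome measures for both regulatory pathways, and sections 34.2 (USA) and 34.3 (EU) repeat the list. It includes fasting glucose, "Glycated hemoglobin (HbA1c"), "Lipid profile (Assess total non-HDL cholesterol, and HDL to total cholesterol ratio"), "Waist and hip circumferences (This will only be performed at the USA sites") and BMI. Section 6.13 says of the blood assays: "These are being analyzed as secondary (i.e. hypothesis generating) endpoints". It gives their purpose as detecting change in cardiovascular risk factors: "Specifically, glycemic control, lipid profile and inflammation are assessed using these tests". The method is in section 34.1, Methods: Secondary Aims: "For each continuous and categorical variable at each time point, we will use a two-sample t-test and" Fisher's exact test, for the two variable types respectively.

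**SAP.** Section 2.2.3 places fasting glucose and HbA1c (as laboratory data) and waist/hip and BMI (as vital signs) under safety: "The safety of subjects will be assessed through summaries and descriptive comparisons between treatment groups on the following safety data". Section 12.2 gives the analysis: "Laboratory data and vital signs as listed in section 2.2.3 will be summarized per treatment group at baseline and per time point on study", with a change-from-baseline summary for the laboratory tests. Section 12.2 uses the Safety Analysis Set throughout. Section 7 defines that set as randomised subjects with at least one session of use, classified by treatment received.

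The blood endpoints given a linear model in section 12.1.3 are LDL, the atherogenic index (total cholesterol to HDL) and hs-CRP. The other secondary comparisons named in section 2.2.2.2 are trunk fat and bone mineral content. Non-HDL cholesterol does not appear.

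**The concern.** The protocol asks whether the device changes glycaemic control, lipids and inflammation relative to sham. Under the SAP, inflammation and part of the lipid question get a baseline-adjusted ITT estimate. Neither glycaemic measure does, nor does non-HDL cholesterol or waist/hip. What is planned for glucose, HbA1c and waist/hip is a set of arm-level summaries grouped by device received, with no stated treatment difference and no interval.

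Two things are at stake. A reader of the report would have no prespecified randomised estimate for these outcomes. Any comparison added later to fill the gap would be chosen after unblinding.

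**Working it through.** The plan states no figure on this point, so there is none to reproduce. The check is a comparison of the two documents, followed by the precision available.

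**Outcome by outcome**

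| Outcome | Protocol 18.3, 34.2, 34.3 | SAP |
|---|---|---|
| Fasting glucose | Secondary; t-test | Safety, summarised (2.2.3, 12.2) |
| HbA1c | Secondary; t-test | Safety, summarised (2.2.3, 12.2) |
| Non-HDL cholesterol | Secondary; t-test | Absent |
| HDL/total cholesterol ratio | Secondary; t-test | ITT linear model, as the inverse ratio (12.1.3) |
| hs-CRP | Secondary; t-test | ITT linear model (12.1.3) |
| Waist/hip (USA sites) | Secondary; t-test | Safety, summarised (2.2.3, 12.2) |
| BMI | Secondary; t-test | Safety, summarised (2.2.3, 12.2) |

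**BMI drops out of the concern.** The schedule of events (protocol 6.4) measures height at Visit 1 only. With height h fixed, percentage BMI loss = (W0/h² − W6/h²)/(W0/h²) = (W0 − W6)/W0, where W0 and W6 are weight at baseline and 6 months. That is percentage weight loss, which already has the primary ITT model.

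**Does the general sentence in SAP section 4 cover the rest?** It says the remaining secondary endpoints will be summarised and analysed, but it names no variable or model. The same section then places laboratory measurements and vital signs under safety.

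**Precision available.** In SD units, 95% half-width = 1.96 × √(2/n) × √(1 − r²), where n is the number per arm and r is the correlation between baseline and 6-month values. The planned n is 90 per arm (SAP section 3). The values of r are assumptions, because the documents give none.

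- n = 90, r = 0: 1.96 × √(2/90) = 0.29 SD
- n = 90, r = 0.6: 0.292 × 0.8 = 0.23 SD
- n = 90, r = 0.8: 0.292 × 0.6 = 0.18 SD

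For waist/hip, protocol section 6 gives about 106 randomised in the USA, which is 200 less the 94 in Northern Ireland. With 10% loss, 106 × 0.9 / 2 = 47.7, or about 48 per arm.

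- n = 48, r = 0: 1.96 × √(2/48) = 0.40 SD
- n = 48, r = 0.6: 0.32 SD
- n = 48, r = 0.8: 0.24 SD

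The 106 is an assumption. The protocol synopsis caps the three USA sites at 106 + 60 + 40 = 206, and SAP section 3 gives 106 + 100 + 40 = 246, with 106 for a single site in both. If more of the 200 come from the USA, the unadjusted half-width falls from 0.40 SD towards the whole-trial 0.29 SD.

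**The case against.** The best defence is that the SAP is carrying out the protocol's own safety objective. Protocol 17.2 includes safety laboratory results, and no separate safety panel is scheduled at 6 months. The glucose and HbA1c assays are therefore natural material for a safety display. This stands as a reason to keep the display. It does not cancel the secondary-outcome listing, the t-test in 34.1 or the purpose stated in 6.13.

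A reader might go further than the documents allow in four ways.

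- **That no information on effect would be reported.** SAP 12.2 does give change-from-baseline summaries by arm for the laboratory tests, and section 9 gives means and SDs. An unadjusted difference could be approximated from these if the number with data is shown. What is missing is the stated difference, its interval, the baseline adjustment and grouping as randomised.
- **That the as-treated set would distort the results.** The two populations differ only by subjects with no recorded session and those given the other device. Secondary outcomes other than weight use observed data in any case. The documents give no reason to expect a large difference.
- **That the lipid question is abandoned.** LDL and the total cholesterol to HDL ratio are modelled. Only non-HDL cholesterol is lost.
- **That section 13 knowingly left the change out.** Section 13 is written against protocol Version 5 of May 2019, and the protocol supplied is Revision 11. Whether Version 5 listed these outcomes in the same way cannot be checked. It can only be said that section 13 does not mention the change.

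**Conclusion.** The point holds for fasting glucose, HbA1c, non-HDL cholesterol and waist/hip. The protocol makes them between-arm secondary outcomes, and the SAP specifies no ITT difference or interval for them. It should be corrected, but its weight is limited. Protocol 34.2 and 34.3 make secondary outcomes outside the labelling list hypothesis-generating only, and none of these four is on that list. Neither regulatory pathway's success criteria, the labelling sequence nor the type I error depends on them. BMI needs no model of its own.

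The half-widths describe the precision that the missing comparisons could offer; they do not measure harm. They rest on 90 per arm with data, the assumed correlations and, for waist/hip, the assumed 106 USA subjects. The documents give no SDs for these outcomes, so the half-widths cannot be put in clinical units.

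**What to change.** In SAP 12.1.3, add change from baseline at 6 months in fasting glucose, HbA1c, non-HDL cholesterol and, at USA sites, waist and hip circumference. Use the linear model already specified for the other blood endpoints: treatment, gender and baseline value, on the ITT population as randomised. Report the LS mean difference with its 95% CI, and label each result hypothesis-generating and outside the labelling sequence. Non-HDL cholesterol is total cholesterol minus HDL, and both are already needed for the atherogenic index.

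Keep the summaries in 12.2. Record the reclassification in section 13, with its reason, and note there that non-HDL cholesterol had been left out and is restored.

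The cost is a few additional model runs on data already collected. The downside is a few more exploratory comparisons, which the label keeps in proportion. The change should be made before unblinding so that the comparisons are prespecified.
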